3. The electrodes will be placed percutaneously in the external ear with the help of a transilluminator to visualize the neurovascular bundles. Three electrodes will be placed on the ventral and one on the dorsal aspect of the ear. The exact location of the implantation may vary slightly from person to person but is determined by both knowledge of auricular neuro-anatomy and visualization of the neurovascular bundles by transillumination. The electrodes will be taped and secured behind the ear next to the generator itself which is secured to the skin with adhesive. The placement of the devices is within standard of care by properly trained medical doctors as already performed as part of separate, ongoing IRB-approved trial at CHW (CHW14/208; clinicaltrials.gov #NCT02367729).
4. The device will then be activated. Sham devices will appear to be activated, though will not cause neurostimulation, in order to maintain impartiality of the investigators as the status of the device will not be apparent.

5. Device placement will take approximately 5 minutes. The patient will remain at rest for the next 5 minutes in the pre-operative area. Care will be taken not to interfere with standard pre-operative procedures.
6. Patients will be advised not to manipulate the device or immerse the device in water as it is water resistant but not water proof. If showering or washing hair, they should place a dry wash cloth or plastic covering over the area to protect the device.

*Randomization Protocol, Material Storage, and Blinding*

Subjects will be randomized in a 1:1 ratio to either active or inactive group. Randomization will be determined using a computer program based on random number generation in blocks of 10 subjects at a time. The manufacturer will provide the researchers with one device per package and each package will have a serial number. The inactive devices will be custom-made by the physical manufacturer, Key Electronics, Jeffersonville, IN, and will be identical in every way to the active device except it will lack the battery. The devices will be "made to order" when requested by the PI and will be shipped and packaged as above. Both the subjects and the doctors placing the devices will be blinded, as the active and inactive devices will look identical with identical packaging and placement procedures.

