The research coordinator (KH) will have the key for unblinding. In an emergency, the PI will also be able to access the key if needed. All other research coordinators, investigators, statisticians and nurses involved will be blinded as to group assignment. The devices will be stored in the manufacturer's packaging and labeled with a serial number and patient ID number. The devices will be stored in a locked office in the Division of Colorectal Surgery, only accessible by research coordinators. Accompanying folders containing all required study materials (VAS, STAI, and PONV score sheets) for each patient will be stored similarly, adjacent to the devices. The unblinded research coordinator (KH) will prepare the subject packages (device and folder) as per randomization scheme. A blinded study team member will bring each subject's numbered package to the pre-operative area when patient arrives on day of surgery. This team member will ask the subject to complete the pre-operative questionnaires and hand the device (numbered with serial # and patient ID only) to one of the certified MDs for placement.

*Intraoperative and Postoperative Protocol*

Neurostimulation will be delivered below sensation threshold continuously for 5 consecutive days, the duration of the device battery. The anesthesiology team will be informed in the preoperative area of participation in the study prior to BRIDGE application. It will be discussed that any use of regional anesthesia or NSAIDs are not permitted in this study. If the anesthesiologist believes the patient has contraindications to other methods of analgesia or anesthesia, or if it may be in the patient's best interest to incorporate regional anesthetic techniques, the patient will be excluded from the study. Operating room staff will be instructed to avoid manipulating the device while moving patient or during procedure. The device does not interfere with any monitoring routinely used in the operating room.

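### Blinded staff handle devices showing the supplier's serial number, and the PI orders them; nothing in the protocol prevents that number from tracking device type

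*Protocol*

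**What the plan says.** All of this is in the Protocol, Day of Surgery/First Day of Participation, mostly in the subsection Randomization Protocol, Material Storage, and Blinding.

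- **Supply.** "The manufacturer will provide the researchers with one device per package and each package will have a serial number".
- **Origin.** "The inactive devices will be custom-made by the physical manufacturer, Key Electronics, Jeffersonville, IN". They are to match the active device in everything but the battery. The active device is described earlier in the same section as a commercial product.
- **Ordering.** Devices are made to order "when requested by the PI and will be shipped and packaged as above".
- **Storage.** "The devices will be stored in the manufacturer's packaging and labeled with a serial number and patient ID number". The locked office is open only to research coordinators, of whom one is unblinded.
- **Hand-over.** The unblinded coordinator prepares each package. A blinded team member takes it to the pre-operative area, has the patient fill in the baseline questionnaires, and is to "hand the device (numbered with serial # and patient ID only) to one of the certified MDs for placement".
- **Blinding.** One coordinator holds the key. "In an emergency, the PI will also be able to access the key if needed". The next sentence reads "All other research coordinators, investigators, statisticians and nurses involved will be blinded as to group assignment". The stated ground for blinding patients and placing doctors is that the two device types share the same look, packaging and way of being placed.

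**The concern.** Matching appearance protects a blind only if nothing else visible on the unit differs by arm. Here a supplier's number stays in view of people who are meant not to know the allocation, and the two device types do not have the same origin. If the numbers were issued in separate runs, a pattern could be noticed without anyone opening the key. Learning one patient's allocation could then inform guesses about others.

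The PI's position adds a second path. A person who requests custom-made sham units may come to see papers that link serial numbers to type. The same person may take devices off and may make the day-30 outcome call.

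The trial relies on its sham, and several of its outcomes are subjective scores taken by study staff. Knowledge of allocation among those staff could affect how scores are asked for and recorded.

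**Working it through.** The plan gives no figure on this point to reproduce, so the check sets the provisions side by side and sizes the two possible cases.

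**1. Who sees the serial number.** The storage and hand-over provisions put it on the package and on the device as handed over. The blinded team member and the blinded placing doctor both handle it. Blinded coordinators also have access to the office where packages are kept, each pairing a serial with a patient ID. No step masks the serial or substitutes a study number.

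**2. Whether the number can carry information on type.** A number unique to each package is not in itself a group code. It is informative only if numbering differs by type, or if someone sees a list linking the two. Custom-made units on one side and a commercial product on the other make separate numbering possible. The documents do not say how numbers are assigned across types.

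**3. Whether the PI is meant to be blinded.** This is inferred. Emergency-only access to the key makes sense only if the PI does not otherwise know. The device instructions also have sham units appear switched on so that investigators stay impartial. The sentence declaring investigators blinded says *other* and follows the one on the PI's emergency access, so it does not settle the matter alone.

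**4. Size.** Inputs: 1:1 allocation and blocks of 10 (Protocol, same subsection); 28 per group (SAP, Power).

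- *Serials unrelated to type.* A block of 10 at 1:1 holds 5 of each type. Before any device is revealed, each is of a given type with probability 5/10 = 0.50. After one is revealed, each other member of its block is of the same type with probability (5 − 1)/(10 − 1) = 4/9 = 0.44. No other device is identified with certainty. This small shift comes from the block, not the label. What remains is any order or shipping record that links serial to type.
- *Serials separated by type (assumption).* Planned devices: 28 + 28 = 56. One revealed device could help classify up to 56 − 1 = 55 others. This upper limit needs clearly separate ranges and someone who knows the other patients' serials.

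**5. Which outcomes are within reach.** Under Intraoperative and Postoperative Protocol, the study team records STAI and PONV daily, while nurses record VAS in hospital. Study personnel repeat all three scores at the first follow-up visit. The coordinator, PI or co-PI makes the day-30 call, covering the scores and narcotic use and refills. Under Device Removal, study personnel obtain the scores by telephone after early discharge, and the PI may remove devices. The main comparison in the SAP, total hospital narcotic requirement, is extracted from the medical record, and the SAP's pain analysis covers the hospital stay. The route therefore bears most directly on PONV (part of Aim 2), STAI, and scores and narcotic data gathered after discharge.

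**The case against.** The strongest reply is that no leak is shown. Inactive units are described as the same as active ones apart from the battery, in the same packaging. The label at hand-over is limited to two numbers, which reads as a deliberate exclusion of group information. Packages are prepared by the one unblinded coordinator and kept under lock. Asking for devices does not disclose their serials, and no provision has the PI receive shipments or packing lists.

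Much of this stands, and it rules out several stronger readings that a reader might infer:

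- *That the label reveals allocation.* This needs numbering that differs by type, or a visible link list. The documents state neither.
- *That the PI orders only the inactive units.* The ordering sentence speaks of the devices in general, straight after one comparing both types, and may cover both.
- *That treating clinicians could adjust analgesia, diet or discharge by serial number.* The number is shown on the package and at hand-over before surgery. Nothing shows that ward nurses or the primary team see it, or that placing doctors belong to that team.
- *That all 56 patients would be exposed.* That is the limit of one assumed case, not an expected result.

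The reply does not supply a safeguard against informative numbering. Identical appearance says nothing about serials, and the lock does not keep out blinded coordinators.

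Relabelling also leaves one gap: if the key is a single full list, opening it in an emergency exposes other patients whatever the label shows. The documents do not describe a single-patient code break.

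**Conclusion.** The point holds as an unaddressed risk to the blind, not as a demonstrated failure of it. Blinded staff and the placing doctor handle the supplier's serial number, the PI requests the devices, and the stated safeguard does not deal with numbering or order papers.

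The size runs from almost nothing beyond order and shipping records, if serials are interleaved, to as many as 55 further devices classified from one, if they separate by type. The documents do not allow a choice between these cases, and the resulting bias cannot be calculated.

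The conclusion rests on two inferences: that the PI is meant to be blinded outside emergencies, and that different origins make separate numbering plausible. The link to outcomes runs through study personnel and the PI. It also assumes that those who learn a device's type take part in later scoring, which the documents permit but do not state. The change should be made because it protects the blind however the units are numbered and costs little.

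**What to change.** Amend the Protocol subsection on randomization, storage and blinding as follows.

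1. The unblinded research coordinator, not the PI, orders, receives and logs both device types.
2. Before a package leaves that coordinator, the serial on both package and device is covered with a study number unrelated to type. Blinded staff and the placing doctor see only that number and the patient ID.
3. The list linking serial to study number is held with the key.
4. Order and shipping papers are kept from the PI and all other blinded staff.

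The cost is one relabelling step and a log, both falling to the coordinator who already prepares every package. The small downside is that tracing a faulty unit requires the link list.

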#### **Exclusion Criteria**

- History of chronic pain disorder (requiring continuous narcotic and/or NSAID use in the week prior to surgery), or active opiate abuse
- Need for emergent procedure, regional anesthesia (does not include escalation of medical management of pain), admission to ICU
- Prolonged postoperative intubation
- Use of intraoperative ketamine or lidocaine drips
- Refusal to receive follow-up phone calls
- Tape allergy/sensitivity
- Latex allergy
- Active pregnancy
- History of seizures
- History of cerebral aneurysm
- Recent organ transplant recipient
- Myocardial infarction within 6 months of study
- Anticoagulation (requiring fully therapeutic anticoagulant, not including anti-platelet agents such as aspirin or clopidogrel)
- Blood clotting disorder
- Other implantable devices/ on-demand electronic device
- MRI planned during study period
- Psoriasis, dermatitis, skin infections around ear

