The patient will undergo general anesthesia per standard of care. There will be no intraoperative or postoperative use of nonsteroidal anti-inflammatory medications (NSAIDs) (i.e. ketorolac, ibuprofen, diclofenac) or regional pain therapies (i.e. epidural anesthesia, transversus abdominis plan blocks); anesthetic plan will otherwise be per treating physician. Once the procedure is over and the patient is extubated and transferred to the postoperative care unit, the patient will continue to receive postoperative pain control per standard of care, as determined by the anesthesia and surgical teams. Auricular neurostimulation has been postulated to decrease the inflammatory response. As NSAIDs (Non-steroidal anti-inflammatory drugs) have a direct inhibitory effect on the inflammatory response, the use of these medications would have a variable effect on the measurement of inflammatory markers and the biological response to surgery. Additionally, NSAIDs are known to have an analgesic effect, which will confound the primary outcome - opioid medication use. Acetaminophen has a benign side effect profile, so the majority will have this included in their regimen. However, NSAIDs have significant risks of kidney injury and bleeding and a large proportion of patients are not eligible. While this would be ideally be randomly distributed between groups; however, in such small study there is risk of imbalanced use that could

further confound our results. Therefore, the postoperative pain regimen will remain standardized for all patients: hydromorphone PCA (no basal rate) while NPO, oxycodone 5-10mg PO q6h PRN once tolerating a diet, and acetaminophen PRN as determined by the primary team.

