Title of Study: Auricular Percutaneous Electrical Nerve Field Stimulation for Postoperative Pain Control in Adults

NCT number: NCT02892513

Document Date: 10/4/2016

Auricular Percutaneous Electrical Nerve Field Stimulation for Postoperative Pain Control in Adults

Statistical analysis plan

Missing Data Handling

Every effort will be made to avoid missing data. Using logistic regression (LR), the assumption of missing at random data will be explored. If the data appear missing at random (MAR), multiple imputations for items and longitudinally random effects models will be used. If missing data appear not random, a sensitivity analysis will be employed, using clinical information and different assumptions to substitute values and see how results are affected.

Patient Demographics and Characteristics Data

Patient characteristics at baseline, demographic and disease characteristics will be summarized using descriptive statistics. In addition, previous and concomitant diseases and medications will be summarized. Frequencies will be presented for the categorical variables (e.g. race) and descriptive statistics will be presented for continuous variables (e.g. age).

Efficacy Variables

Aim 1 (Primary): To determine if auricular neurostimulation reduces visual analog pain scores and promotes decreased opioid usage, as measured by total hospital narcotic requirement in oral morphine equivalents.

Aim 2: To determine if auricular neurostimulation is associated with decreased postoperative nausea and vomiting, postoperative ileus, respiratory depression, and length of hospital stay.

Aim 3: To determine if auricular neurostimulation alters the biologic response to surgery.

Statistical Method

All efficacy data will be analyzed including modified intention to treat (mITT) patients. Per-protocol analysis will be done only if more than 10% of the ITT patients do not qualify for the per-protocol analysis. For all efficacy variables, the baseline value will be defined as the last value taken prior to the start of randomized study.

Continuous/Ordinal variables

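### NSAIDs are barred to protect the Aim 3 markers, but systemic corticosteroids are neither named for collection nor used in the unadjusted Aim 3 test, at a cost in precision and interpretability for a secondary aim

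*Protocol*

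**What the plan says.** - **Reason for the NSAID bar.** Protocol, Intraoperative and Postoperative Protocol: NSAIDs are not allowed during or after surgery because "the use of these medications would have a variable effect on the measurement of inflammatory markers and the biological response to surgery". A second reason is that their analgesic action would confound opioid use, the primary outcome. A third is that "in such small study there is risk of imbalanced use that could" add confounding.
- **What stays open.** In the same section, apart from NSAIDs and regional techniques, "anesthetic plan will otherwise be per treating physician". The Exclusion Criteria add "Use of intraoperative ketamine or lidocaine drips". Corticosteroids appear in neither document.
- **What is collected.** The protocol's Data Collection list covers narcotics, pain rescue and complications, but has no item for corticosteroids. The SAP says that "previous and concomitant diseases and medications will be summarized".
- **Samples.** Blood and a buccal swab are taken before surgery, then twice a day for four days and once on the fifth morning.
- **Analysis.** The SAP states "Aim 3: To determine if auricular neurostimulation alters the biologic response to surgery". It names no marker, time point or model. Continuous variables are compared by Student's t-test, after transformation if needed, or by a Mann-Whitney test. Randomisation is 1:1 in blocks of 10, with no stratification stated.

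**The concern.** The protocol makes two arguments about NSAIDs: an anti-inflammatory drug disturbs the markers, and in a small study its use may be uneven by chance. Both carry over to systemic corticosteroids, whether taken at home, given during surgery or given afterwards. (That they are anti-inflammatory is general clinical knowledge; the documents do not discuss them.) For NSAIDs the plan acts on the argument. For steroids it has no named data item and no place in the Aim 3 comparison.

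At stake is how well Aim 3 can be read. Steroid exposure adds variance to the marker contrast. If exposure turns out uneven, the plan offers no pre-specified way to take it into account, so any later adjustment would be post hoc. The pre-operative sample, which is the most direct way to remove between-patient variation, is already taken but does not enter the stated tests.

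**Working it through.** **1. The plan's own figure.** The SAP's sample size concerns narcotic use only. Reading the 25% decrease as 25% of the logged mean, the difference is 0.25 × 2.3 = 0.575 with SD 0.58. An exact two-sided t-test at 0.05 with 90% power then needs 23 per group. With 0.25 × log10(180) = 0.564 it needs 24. Both are within 2 of the stated 25. Dropout: 25 / 0.90 = 27.8, so 28 per group and 56 in all. (Whether a 25% decrease should be read that way is a separate question.) No sample size is given for Aim 3.

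**2. Inputs for the steroid question.** From the SAP: n = 28 per arm randomised, 25 after dropout, two-sided 0.05. Assumed, because the documents give none of these:
- the proportion exposed, p, is 0.2 to 0.5;
- exposure lowers a log marker by d = 1 residual SD (range 0.5 to 1.5);
- the true device effect is 0.8 SD.

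**3. Formulas.**
- SD of the between-arm difference in exposure = √(2p(1−p)/n). The 95% range is ±1.96 times this.
- Shift in the marker contrast = d × difference in exposure.
- Added residual variance = p(1−p)d².
- Power: noncentral t with noncentrality 0.8·√(n/2) / √(1 + p(1−p)d²) and 2n−2 degrees of freedom. At n = 28 this is 0.8 × √14 = 2.99 with no steroid variance, and 2.99 / √1.25 = 2.68 at p = 0.5, d = 1.

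**4. Results at d = 1.** The exposure and shift columns are for 28 per arm.

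| p | SD of exposure difference | 95% range of shift | Added variance | Power, 28 per arm | Power, 25 per arm |
|---|---|---|---|---|---|
| Steroid variance all removed | – | – | 0 | 84% | 79% |
| 0.2 | 10.7 points | ±0.21 SD | 0.16 | 78% | 73% |
| 0.3 | 12.2 points | ±0.24 SD | 0.21 | 76% | 71% |
| 0.5 | 13.4 points | ±0.26 SD | 0.25 | 75% | 70% |
| 0.05 or 0.95 | 5.8 points | ±0.11 SD | 0.05 | 82% | 77% |

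Over p = 0.2 to 0.5 and d = 0.5 to 1.5, unadjusted power at 28 per arm runs from 65% to 82%.

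**5. Validity.** In 4,000 simulated trials per setting, with exposure equally likely in both arms (50%), the unadjusted t-test rejected a true null in 4.9% to 5.2% of trials for d = 0.5 to 1. Its level is intact. Power for 0.8 SD was 81% (d = 0.5) and 75% (d = 1), against 83% with a term for all steroid exposure. This agrees with step 4.

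**6. If exposure truly differs by arm.** With 40% against 60% exposed, the unadjusted false-positive rate for an effect not due to steroid was 6.4% to 9.8%, and about 5% with the steroid term. Nothing in the documents shows such a difference.

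**The case against.** **The test is valid, so adjustment is a preference.** The first half stands. Randomisation protects the comparison on average when exposure is equally likely in both arms. A reader might infer that uneven steroid use could cancel or imitate a device effect. The figures do not support that: a shift of 0.21 to 0.26 SD (0.39 SD at p = 0.5 and d = 1.5) cannot cancel 0.8 SD, and about 0.75 SD is needed for 80% power at 28 per arm. It lowers the chance of detection. Exposure could differ by arm, since the device is on before anaesthesia and Aim 2 expects it to change nausea, but this is only a possibility.

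**The size rests on assumptions.** It does. Exposure of 5% or 95% leaves 82% against 84%.

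**Medications are already covered.** In part. The SAP's summary implies that some medication data will be collected, so it would be wrong to infer that steroid use will go unrecorded. But a descriptive summary requires no dose or time and enters no comparison. The SAP also defines a baseline value for efficacy variables, and an analysis of change could absorb some effect of long-term home steroid use. It does not say that Aim 3 will be analysed that way.

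**The NSAID comparison is incomplete.** True: NSAIDs are also barred to protect the primary outcome, and the imbalance remark follows a point about patients' eligibility for NSAIDs. The marker argument is still a stated reason in its own right.

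**Aspirin.** A reader might see an inconsistency in the wording "not including anti-platelet agents such as aspirin or clopidogrel". That phrase only defines what counts as therapeutic anticoagulation. It is not a ruling on anti-inflammatory drugs, and no point is made of it here.

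**Aim 3 has a larger gap.** It names no marker or time point. That stands, and the steroid term is subordinate to it.

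**Conclusion.** The concern holds as a matter of precision and interpretability in a secondary aim. The plan applies its reasoning about anti-inflammatory drugs to NSAIDs and leaves corticosteroids without a named data item or a role in the Aim 3 analysis. It also leaves the pre-operative sample unused as a covariate.

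Under the assumptions above, the loss is roughly 6 to 9 percentage points of power, both at the 28 per arm randomised and at the 25 left after dropout. The 84% and 79% are ceilings that require all steroid variance to be removed. A main model with pre-operative steroid use alone will not reach them if exposure is mainly intraoperative. The validity of the randomised test is not in question when exposure is equally likely in both arms, and the powered narcotic outcome is not the subject of this point. Whether steroids should be permitted is a clinical matter on which nothing is said here.

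**What to change.** 1. **SAP, main Aim 3 analysis.** Replace the unadjusted test with a linear model on the marker (log scale where needed) with treatment, the pre-operative value of that marker, and pre-operative systemic steroid use (yes/no). Both covariates precede device placement, so adjusting for them is safe. The pre-operative value helps whatever the steroid rate: it cuts residual variance by a factor of about 1 − r², where r is its correlation with the later value (not given in the documents).
2. **Protocol, Data Collection.** Name home, intraoperative and postoperative systemic corticosteroid, each with drug, dose and time.
3. **SAP, one sensitivity analysis.** Add a term for intraoperative corticosteroid and label it as adjusting for a post-randomisation variable.
4. **Postoperative steroid.** Report exposure by arm. Do not drop samples because of it: a dose given for nausea could depend on the device, and dropping those samples would select on a consequence of treatment.

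The cost is one or two degrees of freedom, a few chart fields and some SAP wording. The sample size and patient care do not change.
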